- Updating recruitment process to include posting approved study flyers on social media platforms. Including the Bridge program at Wolfson Childrens Hospital for study flyer placement.
- Updated estimated project timeline.
- Update Inclusion/Exclusion criteria. Modifications to exclusion/inclusion criteria include: "If pt scores <13 on WHO-5 criteria, they MUST currently be enrolled in therapy services to participate."
- Incentive change: A \$30.00 Amazon
 E-Gift Card will be emailed to each
 adolescent-parent dyad after
 completing the post-survey.

4	10/31/22	 Incentive change: A \$30.00 Amazon E-Gift Card will be emailed to the first 30 adolescent-parent dyads that complete the post-intervention survey (Change reflected on flyer). Adding statistician to project team. Goal Number of parent-adolescent dyads in study. Clarified zoom session meeting dates. Updated final question on the post-intervention survey to assess the impact of the moderator ([name]) on the receptiveness of the educational presentation (Reflected on updated questionnaires). 	
5	11/15/22		

Study Summary

Study Title	Promote Healthy Lifestyle Behaviors for Adolescents with Mental Health Conditions
Study Design	Quasi-experimental study with a one group pretest- posttest design
Primary Objective	To evaluate the impact of an online educational program on improving healthy lifestyle knowledge and behaviors (nutrition, physical activity, screen time, and sleep) among adolescents diagnosed with a mental health condition(s) and their parent(s)/ legal guardian(s).
Secondary Objective(s)	1. Educate adolescents with mental health conditions and their family members about ways to improve healthy lifestyle behaviors.
	2. Evaluate an increase in knowledge on healthy lifestyle behaviors after a 45-minute online education session.
	3. Evaluate an increase in healthy lifestyle behaviors after the intervention.

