This project utilizes a one-group pretest-posttest design study for 30 adolescents (aged 12-17 years) diagnosed with a mental health condition(s) and their parent/legal guardian. This project will implement best practices to promote healthy lifestyle knowledge and behaviors to adolescents and their parent(s)/legal guardian(s). This will be a 45-minute educational presentation delivered via Zoom. Participants can select between multiple dates/times (over a 3-week period) for the educational session. We will compare the effects of an educational program on healthy lifestyle knowledge and behaviors preand post-program (after one month) via a REDCap survey for the adolescent and their parent/legal guardian. The survey will utilize an adapted version of the 2021 National Youth Risk Behavior Survey (YRBS) and the 2020 National Survey of Children's Health (NSCH-T3). The analysis of this project will compare changes in healthy lifestyle knowledge and behaviors using a paired t-test. The educational presentation will be recorded and emailed to participants within 1 week of intervention to re-watch/review.

The educational program will promote a healthy lifestyle knowledge and behaviors through education established by the Centers for Disease Control and Prevention, the World Health Organization, and the American Academy of Pediatrics. Educational sessions will include the importance of healthy lifestyle modifications in the adolescent population with a mental health condition(s), lifestyle recommendations versus reality, nutrition, physical activity, screen time, and sleep recommendations and guidelines. The educational presentation via Zoom will include: 5-10 minutes of education regarding recommendations versus reality for nutrition, PA, screen time, and sleep, 20-25 minutes of education regarding ways to improve healthy lifestyle knowledge and behaviors. Potential obstacles to consider for this project include the recruitment of thirty applicants for this study and maintaining participant and family involvement in the study from pre-intervention to post-intervention.

- 1.2 Drug/Device Handling: N/A
- 1.3 N/A

Procedures Involved*

1.4 Describe and explain the study design.

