Interventions will be evaluated through a pre- and post-intervention survey regarding parental/adolescent's healthy lifestyle knowledge and behaviors developed from nationally approved health surveys including the National Survey of Children's Health (NSCH), the WHO (Five) Well-Being Index, the Patient Health Questionnaire- 9 (PHQ-9), and the Youth Risk Behavior Surveillance System (YRBSS) (Bureau, n.d.; Kroenke et al., 2001; *CDC*, 2021; *WHO-5 Questionnaires*, n.d.). The World Health Organization (Five) Well-Being Index questions will appear in the REDCap survey as a screening prior to the project survey. This survey is suitable for children nine years and above. If the raw score is below 13 or if the patient has answered 0 to 1 to any of the five items, they will not be allowed to complete the REDCap survey or participate in the project (*The World Health Organisation- Five Well-Being Index (WHO-5)*, n.d.; World Health Organization. Regional Office for Europe, 1998).

The pre- and post-intervention survey will be the same, except the post-intervention survey will not include demographic questions. The adolescent survey will include 61 questions total: 6 WHO-5 mental health screening, 7 demographics, 2 weight/self-image, 16 nutrition, 10 PA, 12 sleep, 5 screen time, 4 home environment, and 1 comment box for questions regarding nutrition, PA, screen time, and sleep. The parent/legal guardian(s) survey will include 70 questions total: 4 adolescent mental health screening, 11 demographics, 7 evaluating adolescent overall health, 16 nutrition, 10 PA, 12 sleep, 5 screen time, 4 home environment, 1 comment box for questions regarding nutrition, PA, screen time, and sleep. 1 question will be added to the end of the post-intervention survey (for both adolescent and parent/legal guardian surveys) to assess the impact of the Zoom moderator on the educational intervention. See Appendix.

- 1.5 Provide a description of all research procedures being performed and when they are performed, including procedures being performed to monitor subjects for safety or minimize risks.
 - This project utilizes a one-group pretest-posttest design study for 30 adolescents (aged 12-17 years) diagnosed with a mental health condition(s) and their parent/legal guardian.
 - This will be an educational program delivered via a 45-minute presentation delivered via Zoom.
 - Participants can select between multiple dates/times (over a 3-week period) for educational session.

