1.9 N/A

Data and Specimen Banking* N/A

Sharing of Results with Subjects* N/A

Study Timelines*

1.10 Describe:

- Project recruitment will be begin in early October 2022.
- Project recruitment will end November 2022.
- Project pre-survey survey will be sent out the middle to end of November 2022.
- Participants will have 2 weeks to complete pre-survey prior to Zoom educational session. A reminder email will be sent to complete pre-survey.
- An online educational session will be held middle to end of November 2022. Participants can select between multiple dates/times (over a 3-week period) for educational session.
- Participants will be emailed the recorded educational presentation within 1 week of intervention.
- Participants will then receive a post-survey 1 month after educational session.
- Study will be completed by middle/end of December 2022-Early January 2023.
- The duration of an individual subject's participation in the study.
 - o 1 month duration
- The duration anticipated to enroll all study subjects.
 - o 1 month

- The estimated date for the investigators to complete this study (complete primary analyses)
 - Study will be completed by Middle/End of December 2022- Early January 2023

Inclusion and Exclusion Criteria*

- 1.11 Describe how individuals will be screened for eligibility.
 - Adolescents, 12-17 years old, with a clinical diagnosis of a mental health condition(s) and their parent/legal guardian.
 - Examples of eligible diagnosed mental health conditions include major depressive disorder (MDD), generalized anxiety disorder (GAD), attention-deficit disorder (ADD)/ attention deficit hyperactivity disorder (ADHD), bipolar disorder (BPD).
 - Adolescents that score below 13 on the World Health Organization (Five) Well-Being Index survey or if the adolescent has answered 0 to 1 to any of the five items, they will not be allowed to complete the REDCap survey or participate in the project unless they are currently enrolled in outpatient mental health services (Ex: counseling, therapy, partial hospitalization).

Parent(s)/legal guardian(s), 18 years old or order, live with adolescents diagnosed with mental health condition(s)

- 1.12 Describe the criteria that define who will be included or excluded in your final study sample.
 - Inclusion Criteria:
 - o Individuals who are not yet adults (Adolescents 12-17 years old)
 - With diagnosed mental health condition (ex: Depression, Anxiety, ADD/ADHD) more than one year ago.

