 - o Permission can be obtained from an adolescent's legal guardian.
 - The process to determine the authority to consent to the project will be determined by the first question on the parent/legal guardian survey
 - a. "Are you the parent of legal guardian of the adolescent participating in this project?"
 - The survey will then determine the relationship of the parent/legal guardian again in the demographic questions.
 - a. EX: How are you related to this child?

Biological Parent

Stepparent

Grandparent

Legal Guardian

Other: Relative

Other: Non-Relative

- Indicate whether assent will be obtained from all, some, or none of the children. If assent will be obtained from some children, indicate which children will be required to assent.
 - Assent will be obtained from all adolescents participating in the study.
 - o Assent for adolescents 12-13
 - a. Appendix E
 - o Assent for adolescents 14-17
 - a. Appendix F
- When assent of children is obtained describe whether and how it will be documented.
 - Assent will be obtained and documented as the first section of the REDCap survey.
 - PI will be available via email to answer any questions/concerns participants may have regarding the study.

Prospective subjects should electronically affix their agreement to consent by checking "yes" to, "Do you agree to participate in this study," and providing the date on their consent through the REDCap survey.

The REDCap survey will ask:

- a. Do you agree to participate in this study? If they answer yes, it will populate the following prompts:
 - i. Today's date
 - 1. All the following questions will be marked in REDCap as "identifiers" which will limit access to PHI when exporting your data.
 - 2. To maintain privacy, I will not require participants to enter their name for informed consent. If they check "yes" to, "Do you agree to participate in this study," that will be used in lieu of formal name/signature.

Subjects may maintain a copy of their signed, IRB Stamped, consent by downloading a copy of the signed consent from REDCap.

REDCap survey will state, "Copy of informed consent document for download. Please click on PDF document below to download and save to your computer.

Participants will be able to download their survey responses prior to completing the survey.

- b. Consent will be affirmed through REDCap
 - i. The REDCap survey will include a signature of person obtaining authorization (PI) and today's date

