- c. Investigator accesses the informed consent form (ICF) to affirm informed consent, and e-signs their portion.
- d. Participant and investigator each keep a copy of ICF for their research.
- o For those who decline the study, REDCap will provide a message for those who decline.
 - a. The message as follows: Thank you for your interest. If you agree to participate in the future, please let us know. You can close this window or click on submit below."
 - b. They will still have the opportunity to download copy of informed consent.
 - c. A PDF copy of the e-Consent will be automatically saved in the project's file suppository (not in the record), which can be accessed and downloaded by authorized users as needed
 - d. E-Consent Framework will be enabled which:
 - i. Includes a certification page at the end of the survey
 - ii. Requires respondents to review and confirm information an inline PDF copy of the survey to be marked as complete.
 - iii. Allows versioning of a form.

Cognitively Impaired Adults N/A
Adults Unable to Consent N/A
Adults Unable to Consent N/A

Process to Document Consent in Writing Please check attached consents.

Setting

- 2.26 Describe the sites or locations where your research team will conduct the research.
 - Identify where your research team will identify and recruit potential subjects.
 - The setting will be the Intensive Outpatient Behavioral Health Program (IOP) the Partial Hospitalization Program (PHP) and Bridge Program at Wolfson Children's Hospital in Jacksonville, Florida.
 - Study flyers will be posted on various social media platforms.
 - *Identify where research procedures will be performed.*
 - Online via REDCap Survey and Zoom-based educational intervention.
 - Describe the composition and involvement of any community advisory board.
 N/A
 - For research conducted outside of the organization and its affiliates describe:
 - O Site-specific regulations or customs affecting the research for research outside the organization. N/A
 - Local scientific and ethical review structure outside the organization.

 N/A

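### As worded, the plan lets respondents keep a copy of their baseline answers before the same questions are asked again; the possible bias is small, of unknown direction, and cheap to remove

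*Combined protocol and SAP*

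**What the plan says.** All references are to the combined protocol and SAP.

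- **Download.** In the section on subjects who are not yet adults, the plan first lets subjects download their signed consent. It then adds a separate sentence: "Participants will be able to download their survey responses prior to completing the survey".
- **One survey for assent and outcomes.** The same section says: "Assent will be obtained and documented as the first section of the REDCap survey".
- **Review PDF.** The e-Consent Framework, described just after, has a certification page at the end of the survey and this feature: "Requires respondents to review and confirm information an inline PDF copy of the survey to be marked as complete".
- **Repeated items.** Sections 1.4 and 1.6: "The pre- and post-intervention survey will be the same, except the post-intervention survey will not include demographic questions". One question about the Zoom moderator is added at follow-up.
- **Timing.** Study Timelines, section 1.10: "Participants will have 2 weeks to complete pre-survey prior to Zoom educational session", and "Participants will then receive a post-survey 1 month after educational session".
- **Design and analysis.** The Study Summary gives the design as "Quasi-experimental study with a one group pretest- posttest design", with a goal of 30 dyads. Section 1.1: "The analysis of this project will compare changes in healthy lifestyle knowledge and behaviors using a paired t-test". Section 2.17 plans the same test.

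Nothing in the plan limits the use of a saved copy, asks respondents not to look at it, or asks afterwards whether they did.

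**The concern.** Participants need a copy of their consent. They do not need their baseline answers before follow-up. The post-survey is completed online, so someone who kept the file could have it open while answering. The second answer would then depend on the first for reasons unrelated to knowledge or behaviour.

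That matters here because the within-person difference is the only effect estimate. A control group with the same access would show the effect of consulting earlier answers, but this design has none. Any such effect would be counted as the effect of the education session.

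There is a smaller second issue. Section 2.23 tells participants that their answers stay private. The adolescent survey includes WHO-5 and weight/self-image items, and a saved file of those answers fits poorly with that assurance. The documents do not say where such a file would be kept or who could open it, so this supports the change but is not a separate finding.

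**Working it through.** The plan gives no figure on this point, so there is none to reproduce. The goal of 30 dyads has no stated power, effect size or significance level behind it. The check is a reading of the text followed by an illustration under assumptions.

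**Step 1: what can be downloaded.** The consent copy and the survey responses have separate sentences. If the second meant only the consent copy, it would repeat the first. Assent is the first section of the same survey, the certification page comes at its end, and the review PDF is of the survey. A PDF of a survey shown at its end would normally contain the answers. The literal reading is therefore well supported, though not certain.

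**Step 2: overlap.** Section 1.4 lists 16 nutrition, 10 physical activity, 12 sleep, 5 screen time and 4 home environment questions for both adolescents and parents. That is 16 + 10 + 12 + 5 + 4 = 47 questions asked at both times.

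**Step 3: interval.** Follow-up is one month after the session, and the pre-survey has a two-week window before the session. The copy would be somewhat more than a month old when the items are repeated.

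**Step 4: answers shifted in the taught direction.** The documents supply none of the following assumptions: n = 30 pairs, two-sided 5% paired t-test, no true change, 20% to 50% of respondents consulting the copy, and a shift of 0.1 to 0.3 SD of change among them.

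Bias = share consulting × shift.
- Lowest: 0.2 × 0.1 = 0.02 SD
- Highest: 0.5 × 0.3 = 0.15 SD

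The chance of a significant result comes from the noncentral t distribution with 29 degrees of freedom, noncentrality = bias × √30 and critical value 2.045.

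| Bias (SD of change) | Noncentrality | Chance of significance |
|---|---|---|
| 0 | 0 | 5.0% |
| 0.02 | 0.110 | 5.1% |
| 0.10 | 0.548 | 8.3% |
| 0.15 | 0.822 | 12.5% |

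This holds the SD of change at 1. If only some respondents shift, the SD rises slightly; at the top of the range the variance is 1 + 0.5 × 0.5 × 0.3² = 1.0225, and 12.5% becomes 12.3%.

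**Step 5: answers copied.** Suppose instead that a share f repeat their baseline answers, so their change is 0, and the true standardized change is 0.53, which 30 pairs detect with 80% power. Then mean change = (1 − f) × 0.53, and variance = (1 − f) + f(1 − f) × 0.53².

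| f | Mean change | Variance | Mean / SD | Power |
|---|---|---|---|---|
| 0 | 0.53 | 1.000 | 0.530 | 80% |
| 20% | 0.42 | 0.845 | 0.461 | 69% |
| 50% | 0.27 | 0.570 | 0.351 | 46% |

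The two behaviours act in opposite directions, and the documents do not say which would prevail.

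**The case against.** **The sentence may concern only the consent record.** It stands in the consent-documentation text, between statements about downloading the consent form and about affirming consent in REDCap. Its timing, before the survey is completed, also fits a review-and-confirm step. A reader might infer that the plan certainly hands out outcome data, but the documents do not settle that. This objection stands as a limit on the claim. It does not remove the need for a correction, because the words as written cover survey responses.

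**Nothing shows that anyone would use the copy.** Downloading is optional, and the file would have to be kept for over a month. Section 2.23 asks respondents to answer according to what they really do. The gift card in section 2.7 depends on completing the post-survey, not on improving. All of this makes deliberate shifting less likely, though none of it prevents or detects consultation.

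**The direction is open.** A reader might infer that the education effect will be inflated. Copying would shrink it, and seeing earlier answers might also reduce random inconsistency between two self-reports. The documents support no claim of inflation.

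**Larger threats remain.** Repeat testing and social desirability act in an uncontrolled self-report design with or without a file, and removing the download leaves them in place. This stands, and it is why the point is minor.

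**Conclusion.** The point holds as a minor, avoidable weakness. Read literally, the plan itself gives respondents their baseline answers before the same items are repeated, and any effect of consulting them could not be told apart from the effect of the education.

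The size is unknown. The range of 5.1% to 12.5% significant results under no effect rests wholly on the assumed shares and shifts, on 30 complete pairs, and on a two-sided 5% test. A reader might be tempted by a larger figure, such as 18.5% at a bias of 0.20 SD, but the assumed inputs reach only 0.15 SD. The illustrated loss of power from copying is equally conditional. Neither calculation shows that the trial's result will be biased.

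**What to change.** Put consent and assent in their own REDCap instrument and enable the e-Consent Framework only there, so that the downloadable PDF holds the consent and not the answers. Replace the download sentence with:

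> Participants can download their signed consent or assent; survey responses are not available for download before the post-survey closes.

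If the sponsor meant only the consent record, the same sentence makes that clear.

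The cost is a small configuration change and one sentence of text. Participants who want a copy of their answers wait until after the post-survey. If baseline surveys have already been collected under the present set-up, a post-survey question on whether earlier answers were consulted would at least show how often it happened.
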